## 6.5 Dose Assignment

All subjects will be given the combination treatment of TJ004309 20 mg/kg and atezolizumab 1200 mg Q3W. All subjects will be evaluated for antitumor activity on a regular basis as specified in the protocol and their clinical status classified according to RECIST 1.1 and iRECIST. Treatments may continue until clinically significant disease progression, unacceptable toxicity, or subject/Investigator decision to withdraw.

## 6.6 Measures to Minimize Bias: Randomization and Blinding

Part 1 of this study is a single arm non-randomized study.

## 6.7 Study Intervention Compliance

The United States Food and Drug Administration (US FDA) and other applicable regulatory authorities require accounting of all investigational drug received by each study center. Records of drug disposition required include the date received by the center, date administered, quantity administered, and the patient to whom study drug was administered. The Investigator is responsible for the accountability of all used and unused study drug containers and unused study drug.

Each study center is to use a study drug accountability log to document study drug disposition. All items on this form are to be completed in full. The Sponsor's Clinical Research Associate (CRA) is to approve the area where study drug is to be stored and accountability records are to be maintained.

The Investigator identification number and patient initials (as allowed by local regulations) and identification number are to be recorded on each study drug accountability log. Each time study personnel dispense study drug for a patient, he or she is to record the date dispensed, amount of study drug dispensed, and his or her initials. Study personnel are to monitor the inventory of clinical supplies and maintain a count of all used and unused study drug. The CRA is to review study drug accountability records and remaining drug supplies during routine monitoring visits.

## 6.8 Concomitant Therapy

All prescription and non-prescription medications and therapies, including pharmacologic doses of vitamins, herbal medicines, or other non-traditional medicines, taken from 28 days prior to the first study drug dose are to be documented as *prior* medications. Medications taken from the time of the first study drug dose on C1D1 through 30 days after the last study drug dose are to be recorded as *concomitant* medications in the electronic case report form (eCRF). All therapies for primary diagnosis should be recorded regardless of when they were taken.

### 6.8.1 Prohibited Concomitant Medications

The following medications and treatments are prohibited during study participation:

- Any commercially available or investigational anti-cancer therapy other than the study treatment
- Radiation therapy is prohibited within 2 weeks prior to study Cycle 1 Day 1 and during study treatment. NOTE: Palliative radiation therapy to a small field outside of the target lesion area >1 week prior to Day 1 of the study treatment may be allowed at the discretion of the Investigator or palliative radiation therapy during the protocol may be permitted after discussion with the Sponsor's Medical Monitor.
- Prophylactic granulocyte colony-stimulating factor (GCSF) or GM-CSF is not permitted. The use of these may only be permitted after discussion with the Sponsor's Medical Monitor if indicated.
- Chronic or systemic corticosteroid use (prednisone  $\geq$ 10 mg/day or dexamethasone  $\geq$ 1.5 mg/day) for supportive care is not permitted. (However, acute use to manage suspected immune-related AEs is allowed; however, in such cases, systemic steroid should be stopped at least 24 hours prior to the next dose of the study drug and the use of such needs to be clearly documented in the applicable source docs and CRF). Acute use of topical corticosteroid preparations, inhaled sprays, eye drops, or local injections of corticosteroids are acceptable. Use of a corticosteroid due to a confirmed allergy to IV contrast is also permitted.
- Live vaccines administered within 30 days prior to the initially dose of study drug and while participating in the study are not permitted. Seasonal influenza vaccines for injection that are killed virus vaccines are allowed; live attenuated vaccines such as the intranasal influenza vaccine (e.g., FluMist®) are not allowed. Other types of vaccines (mRNA) may have exemptions, such as the SARS-CoV-2 (COVID-19) vaccine; Sponsor will provide up-to-date guidance based on current practices.
- Subjects are required to refrain from donation of blood from 3 months prior to Screening, plasma from 2 weeks prior to Screening, and platelets from 6 weeks prior to Screening until 3 months after the last Follow-up visit.

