7. Major surgical procedure or significant traumatic injury within 4 weeks prior to study treatment, and must have fully recovered from any such procedure; and no date of surgery (if applicable) or anticipated need for a major surgical procedure planned within the next 6 months (The following situations are not considered to be major procedures and are permitted up to 7 days prior to study treatment: thoracentesis, paracentesis, port placement, laparoscopy, thoracoscopy, tube thoracostomy, bronchoscopy, endoscopic ultrasonographic procedures, mediastinoscopy, incisional biopsies, and routine dental procedures. Core biopsy and skin biopsy do not require a waiting period prior to dosing.)
8. Chest radiotherapy  $\leq$  28 days, wide field radiotherapy  $\leq$  28 days (defined as > 50% of volume of pelvic bones or equivalent), or limited field radiation for palliation  $\leq$  14 days prior to study treatment
9. Pleural effusion or ascites that requires paracentesis in the last 30 days

10. Brain involvement with cancer, spinal cord compression, carcinomatous meningitis, or new evidence of brain or leptomeningeal disease; unless the lesion(s) have been radiated or resected, are considered fully treated and inactive, are asymptomatic, and no steroids have been administered for CNS disease over the 7 days prior to study treatment
11. Angina, myocardial infarction (MI), symptomatic congestive heart failure, cerebrovascular accident, transient ischemic attack (TIA), arterial embolism, pulmonary embolism, percutaneous transluminal coronary angioplasty (PTCA), or coronary artery bypass grafting (CABG) within 6 months prior to study treatment
12. Thrombolytic use (except to maintain IV catheters) within 10 days prior study treatment
13. Known active or chronic Hepatitis B or Hepatitis C, other hepatitides (non-alcohol steatohepatitis, alcohol or drug-related, autoimmune) serology at screening or cirrhosis
14. Any active infection requiring parenteral treatment
15. History of hemorrhage or hemoptysis (> ½ teaspoon bright red blood) within 3 months prior to study treatment
16. Known human immunodeficiency virus (HIV) unless CD4+ T cell count > 350 cells/ $\mu$ L with an undetectable viral load

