### 10.2 Protocol Deviations and Amendments

The Investigator must adhere to the protocol as detailed in this document. The Investigator will be responsible for enrolling only those subjects who have met protocol eligibility criteria. The Investigators will be required to sign an Investigator Agreement to confirm acceptance and willingness to comply with the study protocol. The Investigator should document and explain any protocol deviations in source. The Investigator should promptly report any deviations to the Sponsor or designee, and to the IRB/EC in accordance with established IRB/EC policies and procedures. The Sponsor or designee will review all protocol deviations and conduct impact assessments as needed. As per the Sponsor's standard operating procedures, prospective requests

to deviate from the protocol, including requests to waive protocol eligibility criteria, are not allowed and will not be granted.

All protocol revisions (amendments) must originate with and be documented by the Sponsor. The Investigator must submit all amendments to his/her IRB for review and approval prior to implementation; documentation of approval signed by the chairperson or designee must be sent to the Sponsor.

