##### Non-measurable disease

All other lesions, including small lesions (longest diameter  $< 10$  mm or pathological lymph nodes with  $\geq 10$  to  $< 15$  mm short axis) as well as truly non-measurable lesions. Lesions considered truly non-measurable include: leptomeningeal disease, ascites, pleural or pericardial effusion,

inflammatory breast disease, lymphangitic involvement of skin or lung. Bone lesions, cystic lesions, and lesions previously treated with local therapy require particular comment.

*Bone lesions:*

- Bone scan, PET scan, or plain films are not considered adequate imaging techniques to measure bone lesions.
- Lytic bone lesions, or mixed lytic-blastic lesions, with identifiable soft tissue components, that can be evaluated by cross sectional imaging techniques such as CT or MRI can be considered as measurable lesions if the soft tissue component meets the definition of measurability described above.
- Blastic bone lesions are non-measurable.

*Cystic lesions:*

- Lesions that meet radiographic criteria for simple cysts should not be considered malignant lesions (neither measurable nor non-measurable).
- “Cystic lesions” thought to be cystic metastases can be considered as measurable lesions, if they meet the definition of measurability. However, if non-cystic lesions are present in the same participants, these should be preferably selected for assessment.

Lesions with prior local treatment:

- Tumor lesions situated in a previously irradiated area, or in an area subjected to other loco-situated in a previously irradiated area, or in an area subjected to other loco-regional therapy, are usually not considered measurable unless there has been demonstrated progression in the lesion.

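### Protocol 6.8.1 and exclusion 8 conflict on palliative radiation 8 to 14 days before Day 1, and the SAP has no response rule for a target lesion irradiated on study

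*Protocol*

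**What the plan says.** **Before Day 1.** Exclusion 8 (Protocol 5.2, repeated in the synopsis) rules out a patient who has had "limited field radiation for palliation $\leq$ 14 days prior to study treatment". It gives no exception. It sets a separate 28-day limit for chest and wide-field radiation. Protocol 6.8.1 opens with a general ban: "Radiation therapy is prohibited within 2 weeks prior to study Cycle 1 Day 1 and during study treatment". A note to that ban then makes "Palliative radiation therapy to a small field outside of the target lesion area >1 week prior to Day 1 of the study treatment" permissible if the Investigator so decides. On eligibility, Protocol 10.2 says that "requests to waive protocol eligibility criteria, are not allowed and will not be granted".

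**During the study.** The same note in 6.8.1 goes on: "palliative radiation therapy during the protocol may be permitted after discussion with the Sponsor's Medical Monitor". The restriction to a small field away from the target lesions belongs to the pre-Day 1 clause and is not repeated here.

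**Response analysis.** The primary endpoint is ORR by RECIST 1.1 (Protocol 3.2.1; SAP 2.2.1). SAP 8 uses all tumor response data, unscheduled scans included. SAP 8.1 takes the best overall response from the first dose until progression or the end of treatment, whichever comes first. Neither section mentions radiation. The only RECIST text on irradiated lesions, in Protocol Appendix 1, concerns what may be called measurable: lesions with earlier radiation or "regional therapy, are usually not considered measurable unless there has been demonstrated progression in the lesion".

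**The concern.** There are two separate problems, and only the second bears on the efficacy estimate.

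The first is consistency. A site that reads 6.8.1 alone could accept a patient whom exclusion 8 rules out. The result would be a protocol deviation produced by the protocol's own wording.

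The second is attribution. ORR in a single-arm trial is read as the effect of the study drugs, and no control arm absorbs a response with another cause. If a target lesion can be irradiated on study and later scans still count, the analysis rule itself can credit local treatment to the combination.

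**Working it through.** The plan states no figure on this point, so there is nothing to reproduce. The check sets the passages side by side and then does simple arithmetic.

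**Step 1: the pre-treatment windows.** Let d be the number of days from palliative limited-field radiation to Day 1.
- Exclusion 8: not eligible if d ≤ 14.
- 6.8.1 note: may be allowed if d > 7, for a small field away from the target lesions.
- Both apply when 7 < d ≤ 14, that is on days 8 to 14, a span of 7 days.

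**Step 2: does another passage govern irradiated lesions on study?**
- Appendix 1 on previously treated lesions concerns measurability, and its wording is qualified.
- Appendix 1 on iRECIST treats a need for radiation as a sign of clinical instability, but only when deciding on treatment after RECIST progression.
- Protocol 4.6 and SAP 3.4 end tumor follow-up at a new anti-cancer treatment, but only for patients already off study treatment.
- SAP 4.5.1 counts later radiotherapy as subsequent anti-tumor therapy. SAP 9.1 uses that date to close the adverse-event window; SAP 8.1 does not use it for response.
- SAP 6.7 and 6.12 list prior and subsequent radiotherapy. No dedicated listing covers radiation given during treatment.

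None of these fills the gap.

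**Step 3: when could radiation alone produce a PR?** Appendix 1 requires a fall of at least 30% in the sum of target diameters, with no new lesion and no non-target progression. Assume k target lesions of equal size, one of them irradiated and the rest unchanged. The irradiated lesion must then shrink by 0.30 × k of its own diameter:
- k = 1: 30%
- k = 2: 60%
- k = 3: 90%
- k = 4: 120%, which is impossible; k = 5 likewise

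Inclusion 9 asks for only one measurable lesion, so k = 1 can occur. If the other lesions are also shrinking, less is needed from the irradiated one. SAP 8.1 states no confirmation requirement, although the comparison table in Appendix 1 says that confirmation applies in non-randomised trials. As the SAP is written, one scan after radiation could suffice.

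**Step 4: weight of one such response.**
- In 15 patients: 1/15 = 6.7 percentage points.
- In 30 patients: 1/30 = 3.3 percentage points. For example, 2/30 = 6.7% (95% Clopper-Pearson interval 0.8 to 22.1) becomes 3/30 = 10.0% (2.1 to 26.5).

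**The case against.** The strongest reply on eligibility is that the documents, read together, already decide the case. Protocol 5.2 makes any single exclusion criterion disqualifying, Section 8 requires all criteria to be confirmed at screening, 10.2 refuses waivers, and the 6.8.1 note is only permissive. On that reading this is a drafting inconsistency. It also has no route to ORR bias, because the pre-Day 1 exception keeps the field off the target lesions. This largely stands. It lowers the weight of the first problem but does not remove it, since the note still tells Investigators that they have a discretion which exclusion 8 denies them.

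On response, the reply is that on-study radiation is prohibited by default and needs the Medical Monitor's involvement. BOR also stops at progression, so radiation after RECIST progression cannot create a RECIST 1.1 response. Non-drug interventions are recorded on the CRF (Protocol 6.8.2), and concomitant procedures are summarized (SAP 6.10). All of this is correct. It makes the event uncommon and traceable, but none of it says how a scan after radiation is to be classified.

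A reader might infer three stronger points that the documents do not support:
- **A second conflict for chest or wide-field radiation at 15 to 28 days.** Exclusion 8 is simply stricter there than the two-week ban in 6.8.1. A site can follow both, and the absence of a prohibition in 6.8.1 does not make a patient eligible.
- **Shrinkage of an irradiated target lesion would always count as a response.** Step 3 shows that it could do so only where that lesion carries enough of the target sum, and where there is no new lesion or non-target progression.
- **One such response undermines the Cohort 1 futility decision by moving 2/15 to 3/15.** The rule is worded as something that may or might be applied. SAP 4.1 records that Part 2 was not initiated because too few responses were seen.

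**Conclusion.** Both parts hold in limited form. The protocol contradicts itself on small-field palliative radiation away from target lesions on days 8 to 14 before Day 1. This is a matter of wording, with no demonstrated effect on ORR. The SAP leaves open whether a response reached after on-study radiation to a target lesion counts in the primary endpoint, and as written it would. The exposure is mainly in patients with one to three target lesions, under the equal-size assumption in Step 3. One affected patient shifts ORR by 6.7 points in 15 or 3.3 points in 30. The expected bias cannot be calculated, because the documents give neither a rate of on-study radiation nor the number of target lesions per patient. What remains at stake is the descriptive ORR and its interval in the abbreviated study report.

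**What to change.** **Protocol.** Reconcile exclusion 8 (Section 5.2 and the synopsis) with the note in 6.8.1, so that both give the same answer for days 8 to 14. The interval is for the sponsor to set.

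**SAP 8.1.** Add a rule along these lines: tumor assessments made after on-study radiation to a target lesion do not count toward CR or PR; a response reached before that radiation stands; later assessments still count for progression. A matching line in SAP 8.2 would keep iORR consistent.

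**Listing.** Add a by-subject listing of radiation given during treatment, with its date and whether a target lesion lay in the field. The items that Protocol 6.8.2 names for the CRF do not include the field, so sites may have to be asked about any affected patient.

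**Cost.** A few sentences and one listing, with no added patients or visits. The rule leaves the denominator unchanged and can only lower the response count or leave it as it is. The one downside is therefore a possibly slightly lower ORR, including the loss of a genuine drug response first seen after radiation. Because it cannot favour the study drugs, adding it late carries little risk of bias in their favour.

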#### 6.8.2 Permitted Concomitant Medications

Medications and treatments other than those specified in, including palliative and supportive care for disease-related symptoms, are permitted during the study. Patients should be closely monitored, and treatment is to be instituted for disease-related symptoms, as appropriate.

- All prior medications and non-drug interventions received by subjects within 28 days (4 weeks) prior to the initially dose of study treatment and up to 30 days after the last dose of study treatment will be recorded on the CRF, including the name of the procedure or medication, dose, route, indication and duration of treatment. Concomitant treatment and supportive care considered necessary for the subject's well-being may be given at the discretion of the treating physician using his or her clinical judgment in consultation with the Sponsor.
- Medications (antihistamines, H2-blockers, anti-pyretics, bronchodilators, corticosteroids, and other medically indicated medications) to treat infusion-related reactions are acceptable.
- Medications to treat anemia, thrombocytopenia, and other TJ004309-related adverse effects are permitted.
- Hormone replacement therapy, oral, implantable, transdermal, injectable, or intrauterine contraceptives are acceptable concomitant medications.
- Antiemetic treatments may be used at the Investigator's discretion and in accordance with the American Society of Clinical Oncology guidelines or equivalent after documented nausea or vomiting has occurred without medications having been used.

#### 6.8.3 Premedication

On Cycle 1 Day 1, the following premedication will be administered within 30 minutes to 2 hours prior to the start of the initial TJ004309 infusion:

- Antipyretic (i.e., acetaminophen 650 mg PO)
- Antihistamine (i.e., diphenhydramine 25 to 50 mg PO/IV, cetirizine 10 mg, etc.)

Premedication is not required for subsequent infusions unless a given patient experiences Grade > 2 infusion related reaction with the immediate prior dose of TJ004309.

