### 6.9 Dose Modification and Dose Delays

The treatment management guidelines including dose delay and dose modification of TJ004309 for hematological and non-hematological toxicities are provided in [Table 6](#) and [Table 7](#) respectively. Treatment management guidelines for Immune-Related Adverse Events (irAEs) are provided in [Table 8](#).

Dose delay up to 4 weeks is allowed for subjects with manageable AEs at the Investigator's discretion, e.g., Grade 4 or Grade 3 thrombocytopenia with Grade  $\geq 2$  bleeding, uncomplicated Grade 3 febrile neutropenia, and Grade 4 neutropenia. The Investigator can continue to withhold treatment for up to 12 weeks after the last dose based on the Investigator's medical judgement. If the subject has recovered to Grade  $\leq 1$  or baseline within 12 weeks, continue treatment of TJ004309 at the same dose level. Dose modification or withholding of doses other than as described in this section is not permitted.

If a Grade  $\geq 2$  toxicity recurs for the second time, the Investigator may discuss with the Sponsor whether resuming TJ004309 is appropriate considering the type and grade of the toxicity. If the agreement is to resume TJ004309, treatment can continue to be withheld for up to 12 weeks to allow the subject to recover to Grade  $\leq 1$  or baseline at the Investigator's discretion. If the subject recovers to Grade  $\leq 1$  or baseline within 12 weeks, continue treatment of TJ004309 at the same dose level. If the subject does not recover within 12 weeks, permanently discontinue TJ004309. The Investigator should always manage their subjects according to their medical judgment based on the clinical circumstances.

All dose modifications must be clearly documented in the subjects' source notes and Case Report Form (CRF).

Study treatment dose delays are permitted in the case of medical/surgical events or logistical reasons not related to study therapy (e.g., surgery, unrelated medical events, patient vacation, and/or holidays). Participants should be placed back on study therapy within 28 days of the scheduled interruption, unless otherwise discussed with the Sponsor. The reason for interruption should be documented in the patient's study record. All dose delays must be clearly documented in the patients' source notes and the eCRF.

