**Table 7: TJ004309 Treatment Management Guidelines for Adverse Events (Non-Hematological Toxicities)**

Adverse Event	Grade	Management Actions*
Infusion Related Reactions (IRR) 	Grade 2	
 
Interrupt or slow the rate of infusion. Monitor and if the reaction worsens, stop infusion.
 
Administer institutional standard medications for hypersensitivity reaction as medically indicated. Monitor symptoms until stable. Re-initiate infusion if patient is stable at a 50% slower rate. Prophylactic medications indicated for <math>\leq</math> 24 hours.
 
For subsequent infusions, administer premedication with the following or per institutional standard:           
 
H-1 antihistamine: Diphenhydramine 25-50 mg PO or IV 30 minutes prior to infusion
 
Acetaminophen 500-1000 mg PO 30 minutes prior to infusion
 
Corticosteroids such as dexamethasone (or equivalent) or anti- emetics such as ondansetron (or equivalent) may be administered based on clinical presentation of previous IRR
 
 
 
For subsequent infusions, may administer TJ004309 at a 50% slower rate.
 

	Grade $\geq$ 3	
 
Stop infusion immediately and discontinue TJ004309.
 
Administer epinephrine, bronchodilators, antihistamines, glucocorticoids, IV fluids, vasopressors, oxygen, etc. as medically indicated. Contact sponsor to report SAE.
 
Increase monitoring of vital signs as medically indicated until stable.
 

Chills	Grade 3	
 
Stop the infusion.
 
Administer aggressive symptomatic therapy per institutional standard.
 
After resolution of all symptoms, treatment can be resumed at slower rate, unless severe reaction. If severe reaction, then withhold TJ004309 per Investigator's discretion of clinical presentation of the subject.
 

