	Grade 4	
 
Give supportive care based on Investigator discretion.
 
If the subject has recovered to Grade <math>\leq 1</math> or baseline within 4 weeks, continue treatment of TJ004309 at the same dose level. If the subject has not recovered within 4 weeks, the Investigator can continue to withhold for up to 12 weeks after the last dose based on the Investigator's medical judgement.
 
If recurs for the second time, withhold treatment for up to 12 weeks while giving appropriate medical treatment at the Investigator's discretion. If the subject has recovered to Grade <math>\leq 1</math> or baseline within 12 weeks, continue treatment of TJ004309 at the same dose level. If the subject has not recovered up to 12 weeks, permanently discontinue TJ004309.
 

Other non-hematological adverse reactions	Grade 3	
 
If the subject has recovered to Grade <math>\leq 1</math> or baseline within 4 weeks, continue treatment of TJ004309 at the same dose level. If the subject has not recovered within 4 weeks, the Investigator can continue to withhold for up to 12 weeks after the last dose based on the Investigator's medical judgement.
 
Monitor toxicities weekly until recovered or stable.
 
Give supportive care based on Investigator discretion.
 
Conduct adequate evaluation to confirm etiology and/or exclude other causes.
 
If recurs for the second time, withhold treatment for up to 12 weeks while giving appropriate medical treatment at the Investigator's discretion. If the subject has recovered to Grade <math>\leq 1</math> or baseline within 12 weeks, continue treatment of TJ004309 at the same dose level. If the subject has not recovered up to 12 weeks, permanently discontinue TJ004309.
 

	Grade 4	
 
Discontinue TJ004309.
 

For further information, please refer to the Common Terminology Criteria for Adverse Events v5.0 (CTCAE) at <http://ctep.cancer.gov>

\*Treating physicians' assessment and judgement are critical, and all the management actions should be taken with physician's discretion.

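### Protocol 6.4 and 6.8.3 require later premedication only after a reaction above Grade 2, but Table 7 premedicates after Grade 2 and stops TJ004309 at Grade 3 or higher

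*Protocol*

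**What the plan says.** Premedication with an antipyretic and an antihistamine is mandatory at Cycle 1 Day 1. Protocol 6.8.3 states that "the following premedication will be administered within 30 minutes to 2 hours prior to the start of the initial TJ004309 infusion".

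For later infusions, 6.4 (Treatment Administration) and 6.8.3 (Premedication) contain the same sentence: "Premedication is not required for subsequent infusions unless a given patient experiences Grade > 2 infusion related reaction with the immediate prior dose".

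Table 7 covers infusion related reactions in two rows:

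- **Grade 2.** Interrupt or slow the infusion, treat, and restart at a slower rate once the patient is stable. Then: "For subsequent infusions, administer premedication with the following or per institutional standard". The listed drugs are an H-1 antihistamine and "Acetaminophen 500-1000 mg PO 30 minutes prior to infusion", with a corticosteroid or anti-emetic as an option.
- **Grade 3 or higher.** "Stop infusion immediately and discontinue TJ004309".

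A separate Table 7 row covers Grade 3 chills: "After resolution of all symptoms, treatment can be resumed at slower rate, unless severe reaction". The table's footnote makes its actions subject to the treating physician ("assessment and judgement are critical, and all the management actions should be taken with" their discretion). Section 6.9 refers sites to the tables for "The treatment management guidelines including dose delay and dose modification of TJ004309 for hematological and non-hematological toxicities".

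**The concern.** The two instructions give different defaults for the same patient. After a Grade 2 reaction, a site that opens the section titled Premedication reads that nothing further is required. A site that opens Table 7 reads that it should premedicate. Neither 6.4 nor 6.8.3 refers to Table 7 on this point.

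The threshold also does not fit the rest of the protocol. A trigger above Grade 2 applies mainly to patients whom Table 7 has already taken off TJ004309.

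What is at stake is patient safety at the second and later infusions, at the grade most often seen in Phase 1. In the analysis, a worse reaction at a later infusion could change the maximum-grade, Grade 3 or higher, serious or discontinuation tables (SAP 9.1). A repeat reaction could change the counts of interrupted or slowed infusions (SAP 7).

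**Working it through.** The plan states no figure to reproduce. The check sets the texts side by side and uses the Phase 1 counts from Protocol Table 4 (infusion related reaction row, N = 20) to show which grade matters.

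| Grade of reaction at the prior dose | 6.4 and 6.8.3: later premedication | Table 7 | Phase 1 patients |
|---|---|---|---|
| 1 | Not required | No row | 2 |
| 2 | Not required | Premedicate subsequent infusions | 11 |
| 3 or higher | Required | Discontinue TJ004309 | 0 |

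**Step 1: where the texts disagree.** At Grade 1 there is no conflict. At Grade 2 one text says not required and the other says to give it. At Grade 3 or higher, 6.4 and 6.8.3 call for premedication before an infusion that Table 7 does not allow.

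**Step 2: who the written trigger still reaches.** Two groups remain: patients re-dosed after Grade 3 or higher under the discretion footnote, and patients resumed after Grade 3 chills, if that event is counted as an infusion related reaction (the protocol does not say). The trigger is therefore nearly inoperative, but not empty.

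**Step 3: which grade is common.** The counts sum correctly: 2 + 11 + 0 = 13, and 13/20 = 65%, as Table 4 gives.

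- Patients with a reaction who meet the written trigger (above Grade 2): 0/13.
- Patients with a reaction who meet the Table 7 Grade 2 row: 11/13 = 84.6%.
- Grade 2 rate: 11/20 = 55.0%, Clopper-Pearson 95% CI 31.5% to 76.9%.
- Grade 3 or higher rate: 0/20 = 0%, with upper 95% limit 1 − 0.025^(1/20) = 16.8%.

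With the threshold moved to Grade 2 or higher, the trigger would have been met by 11/13 instead of 0/13.

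**Step 4: duration.** Sections 6.4 and 6.8.3 look only at the immediately preceding dose. Table 7 refers to later infusions in the plural and gives no end point. Take a patient with a Grade 2 reaction at Cycle 1 and none at Cycle 2. At Cycle 3, 6.4 and 6.8.3 require nothing, even with the threshold corrected. Table 7 can be read either way.

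**The case against.** The strongest reply is that no site is put in breach. Not required sets a minimum, so a site that premedicates after Grade 2 complies with every section. The Table 7 row that staff would consult to manage a Grade 2 reaction is the same row that directs later premedication, and 6.9 points to that table. There are other safeguards: under 6.9, a second recurrence of a Grade 2 or higher toxicity may prompt discussion with the sponsor about resuming, and under 6.4 the TJ004309 infusion may be shortened only if there was no reaction at Cycle 2. Phase 1 reactions were Grade 1 or 2 and resolved in subsequent infusions (Protocol 2.5 and 4.3). All of this stands and keeps the point minor. It does not make the default in 6.4 and 6.8.3 right, and physician discretion does not tell a site which default applies.

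A reader might infer three stronger things that the documents do not support:

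- **That Table 7 mandates premedication at every later cycle after any Grade 2 reaction.** It refers to subsequent infusions, but does not say all of them and does not say after a reaction at any earlier dose. The immediate-prior-dose wording could be read as supplying the duration that Table 7 leaves out.
- **That following Table 7 fixes a single regimen.** Its acetaminophen dose and timing differ from Cycle 1 (650 mg, 30 minutes to 2 hours before), but it also allows the institutional standard.
- **That the Phase 1 rate predicts how many patients here are affected.** Phase 1 pooled several doses and schedules with a monotherapy first cycle, and Cycle 1 premedication is mandatory here. The rate may not carry over, so no projection is made.

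The effect on the safety tables is likewise only possible. SAP 9.1 counts a patient once per term at the maximum grade, so a repeat reaction of the same grade leaves the maximum-grade table unchanged.

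**Conclusion.** The premedication trigger in 6.4 and 6.8.3 is wrong as written. It omits Grade 2, the grade that Table 7 premedicates and re-doses. Apart from discretionary re-dosing and the Grade 3 chills row, it names only grades at which TJ004309 is stopped. The 0-versus-11 split among the 13 Phase 1 patients with a reaction shows that the omission falls on the commonest grade. It measures how often the conflicting wording would have applied, not harm.

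This is a minor patient-safety inconsistency. ORR is not affected, and any effect on the safety or infusion-modification tables is likely small. The documents give no figure for the risk of omitting later premedication. The mismatch between the immediate prior dose and subsequent infusions is a secondary ambiguity for the sponsor to settle, not a second proven contradiction.

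The conclusion assumes that Table 7 states the intended clinical rule. The pattern suggests that Grade 2 or higher was meant in 6.4 and 6.8.3, but the documents do not say so.

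**What to change.** In both 6.4 and 6.8.3, change the threshold from Grade > 2 to Grade ≥ 2 and add: see Table 7. This removes the conflict at Grade 2 and keeps the existing requirement for anyone re-dosed after a higher grade.

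In the same edit, the sponsor should decide how long premedication continues after a Grade 2 reaction and use the same words in 6.4, 6.8.3 and Table 7. That is a clinical decision which the present text does not settle.

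The cost is one changed sentence in two sections, one duration phrase, and a site notice if dosing continues. No extra data, patients or SAP changes are needed. The practical value is limited if dosing has ended. SAP 4.1 says Part 2 was not initiated, but does not say whether Part 1 dosing is complete.
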